## 6. Unblinding Plan

#### 6.1. Interim Analyses

No interim analyses are planned for this study. If an unplanned interim analysis is deemed necessary, the appropriate Lilly CRP or CRS, or designee, will be consulted to determine whether it is necessary to amend the protocol.

## 6.2. Site Level Unblinding

This study includes a 16-week double-blind (dulaglutide versus placebo) primary treatment period, and a 36-week open-label extension treatment period.

To preserve the blinding of the study, the treatment assignments in the double-blind period will be blinded to patients and investigators until study completion.

Emergency unblinding for AEs may be performed through the IWRS, which may supplement or take the place of emergency codes generated by a computer drug-labeling system. This option may be used ONLY if the patient's well-being requires knowledge of the patient's treatment assignment. All actions resulting in an unblinding event are recorded and reported by the IWRS. If an investigator, site personnel performing assessments, or patient is unblinded, the patient must be discontinued from the study. In cases where there are ethical reasons to have the patient remain in the study, the investigator must obtain specific approval from a Lilly CRP or CRS for the patient to continue in the study.

In case of an emergency, the investigator has the sole responsibility for determining if unblinding of a patient's treatment assignment is warranted. Patient safety must always be the first consideration in making such a determination. If the investigator decides that unblinding is warranted, the investigator should make every effort to contact the Lilly CRP or CRS prior to unblinding a patient's treatment assignment unless this could delay emergency treatment of the patient. If a patient's treatment assignment is unblinded, Lilly must be notified immediately.

## 6.3. Sponsor/Trial Level Unblinding

The study team will remain blinded to treatment assignments until all patients have completed the study and the database has been finalized and locked for analysis. During this study, some members are unblinded (Table GBGF. 6.1). They do not have direct interaction with sites. They will not be allowed to join meetings which may affect the other members' blind condition, such as trail level safety review (TLSR) and data review meetings.

Role	Reason	Data source for unblinding
Product Delivery personnel	To provide and manage clinical trial materials	e-CTS

#### Table GBGF. 6.1 Unblinded Members through GBGF Study

Unblind Case Manager	To report SAE with unblinded information to Japan authority	e-CTS
Clinical Laboratory Operations	To manage and track sample shipping	CLRM

Abbreviations: CLRM = Clinical Laboratory Results Modernization; e-CTS = Enhanced Clinical Trials System; SAE = Serious Adverse Event.

## 8. Appendices

# Appendix 1. Empirical method for the rate of severe hypoglycemia

Traditionally, Poisson distribution has been assumed to draw inference for the rate of rare events. When the event is rare and the sample size is large, it is known that the overall number of events is approximately from Poisson distribution. However, for some not very rare events such as severe hypoglycemic events in T1DM patients, the total number of events may not be distributed from Poisson and may be over-dispersed. Assuming Poisson distribution may significantly underestimate the variance, and therefore may reduce the overage probability and inflate the Type-I error. Below we describe an empirical method in estimating the variance of event rate without assuming any distribution on the number of events.

#### Event rate without strata

Let  $X_{ij}$  denote the count response variable for patients *j* in treatment group *i*. Let  $Y_i = \sum_j X_{ij}$  be the total number of events for treatment group *i*, and  $T_i$  denote the exposure for treatment group *i*. Let *i* = 0 for the control group and *i* = 1 for the experimental treatment group. The event rate for treatment group *i* can be calculated as

$$\hat{r}_i = \frac{Y_i}{T_i}$$

The empirical variance of  $\hat{r}_i$  is

$$\widehat{Var}(\hat{r}_i) = T_i^{-2}\widehat{Var}(Y_i) = T_i^{-2}n_iS_i^2,$$

where  $S_i^2$  is the variance of  $X_{ij}$  for treatment group *i*. Using the delta-method, the variance of  $log(\hat{r}_i)$  can be estimated as

$$\widehat{Var}(\log(\hat{r}_i)) = Y_i^{-2} n_i S_i^2$$

The relative rate of the experimental treatment versus the control treatment is estimated as

$$\hat{\lambda} = \frac{\hat{r}_1}{\hat{r}_0}$$

The variances of  $\hat{\lambda}$  and  $\log(\hat{\lambda})$  are

$$\widehat{Var}(\hat{\lambda}) = \hat{\lambda}^2 \widehat{Var}(\log(\hat{\lambda}))$$
$$\widehat{Var}(\log(\hat{\lambda})) = \widehat{Var}(\log(\hat{r}_0)) + \widehat{Var}(\log(\hat{r}_1)) = Y_0^{-2} n_0 S_0^2 + Y_1^{-2} n_1 S_1^2$$

Assuming  $\log(\hat{\lambda})$  is asymptotically from a normal distribution, the  $100(1 - \alpha)\%$  confidence interval for  $\log(\hat{\lambda})$  can be constructed as

$$\left[\log(\hat{\lambda}) - z_{1-\frac{\alpha}{2}}\sqrt{\widehat{Var}(\log(\hat{\lambda}))}, \, \log(\hat{\lambda}) + z_{1-\frac{\alpha}{2}}\sqrt{\widehat{Var}(\log(\hat{\lambda}))}\right]$$

Then, the  $100(1 - \alpha)\%$  confidence interval for  $\hat{\lambda}$  is

$$\left[\hat{\lambda}\exp\left(-z_{1-\frac{\alpha}{2}}\sqrt{\widehat{Var}(\log(\hat{\lambda}))}\right), \quad \hat{\lambda}\exp\left(z_{1-\frac{\alpha}{2}}\sqrt{\widehat{Var}(\log(\hat{\lambda}))}\right)\right]$$
(1)

The p-value for testing the null hypothesis of  $H_0: \lambda = 1$  is calculated as

$$p = 2\Phi\left(\left|\log(\hat{\lambda})\right| / \sqrt{\widehat{Var}(\log(\hat{\lambda}))}\right)$$
(2)

where  $\Phi$  is cumulative distribution function of the standard normal distribution.

Event rate with strata or based on multiple studies

We use additional subscript "k" denote the corresponding variable for stratum (or study) k. The Mantel-Haenszel weighted estimate of  $\lambda$  across strata is

$$\hat{\lambda} = \frac{\sum_k w_k \hat{r}_{1k}}{\sum_k w_k \hat{r}_{0k}}$$

where  $w_k = (T_{0,k}^{-1} + T_{1,k}^{-1})^{-1}$ . The variance of  $\log(\hat{\lambda})$  is estimated as

$$\widehat{Var}(\log(\widehat{\lambda})) = \frac{\sum_{k} w_{k}^{2} \widehat{Var}(\widehat{r}_{1k})}{(\sum_{k} w_{k} \widehat{r}_{1k})^{2}} + \frac{\sum_{k} w_{k}^{2} \widehat{Var}(\widehat{r}_{0k})}{(\sum_{k} w_{k} \widehat{r}_{0k})^{2}}$$

The 95% confidence interval for  $\lambda$  and the p-value can be constructed similarly using (1) and (2) as for the ratio rate without strata.

The event rate for each treatment group is

$$\hat{r}_i = \frac{\sum_k w_k \hat{r}_{ik}}{\sum_k w_k}, \qquad i = 0,1$$

and the variance estimation for the event rate is

$$\widehat{Var}(\hat{r}_i) = \frac{\sum_k w_k^2 \widehat{Var}(\hat{r}_{ik})}{(\sum_k w_k)^2}, \qquad i = 0,1$$

Event rate in the cross-over study (no period effect)

For 2 × 2 cross-over study, each patient may receive both treatments, e.g. control treatment in period 1 and experimental treatment in period 2. The above equation of event rate without strata for  $\hat{r}_i$  can still be applied to the calculation of event rate for each treatment group but the variance of relative rate is different from  $Var(\hat{\lambda})$  due to the variance within patient. To distinguished from  $\hat{\lambda}$ ,  $\hat{\lambda}$  is used to indicate the relative rate of the experimental treatment versus the control treatment for the cross-over study

$$\tilde{\lambda} = \frac{\hat{r}_1}{\hat{r}_0}$$

The variances of  $\log(\tilde{\lambda})$  is

$$\begin{split} \widehat{Var}(\log(\tilde{\lambda})) &= \widehat{Var}(\log(\hat{r}_0)) + \widehat{Var}(\log(\hat{r}_1)) - 2\widehat{Cov}(\log(\hat{r}_0),\log((\hat{r}_1))) \\ &= Y_0^{-2}n_0S_0^2 + Y_1^{-2}n_1S_1^2 - Y_0^{-1}Y_1^{-1}\sum_j\widehat{Cov}(X_{0j},X_{1j}) \end{split}$$

Let  $S_c^2$  be the covariance of  $X_{0j}$  and  $X_{1j}$  for patient *j* and identical for all patient, and  $n^*$  be the number of patients who completed both the two cross-over periods, the variance of  $\log(\tilde{\lambda})$  is

$$\widehat{Var}(\log(\tilde{\lambda})) = Y_0^{-2} n_0 S_0^2 + Y_1^{-2} n_1 S_1^2 - Y_0^{-1} Y_1^{-1} n^* S_c^2$$
(3)

With the variance of in (3)  $\log(\tilde{\lambda})$ , the 95% confidence interval for  $\tilde{\lambda}$  and the p-value can be constructed similarly using (1) and (2).

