#### **10.3.4. Safety Analyses**

The safety analyses will include measurements of AEs, SAEs, hypoglycemic episodes, laboratory analytes, vital signs, and ECGs. The safety analyses will be conducted by treatment for 2 periods; primary treatment period and entire study period (including primary, extension, and follow-up periods). Unless otherwise specified, the Safety Population will be used for analyses of safety measurements. P-values provided from all safety analyses will be used for guidance purposes only.

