#### 5.2. General Considerations

Statistical analysis of this study will be the responsibility of Lilly or its designee. Any change to the data analysis methods described in the protocol will require an amendment ONLY if it changes a principal feature of the protocol. Any other change to the data analysis methods described in the protocol, and the justification for making the change, will be described in the clinical study report (CSR). Additional exploratory analyses of the data will be conducted as deemed appropriate.

All analyses will be implemented using Version 9.1.3 SAS or higher.

Continuous data will be summarized in terms of the number of observations (n), mean, standard deviation (SD) and/or standard error of the mean (SEM), median, minimum (Min), and maximum (Max).

Categorical data will be summarized in terms of the number of observations (n), frequency count, and percentages. Percentages will be rounded to one decimal place. Percentages will not be presented for zero counts. Unless noted otherwise, percentages will be calculated using n (the number of observations with non-missing values) as denominator.

For efficacy analysis based on mixed-model for repeated measures (MMRM), summary statistics will be provided for the observed value and change from baseline value for each arm based on MMRM. Also, for efficacy analysis, statistical tests (including MMRM and ANCOVA) will only be conducted during the double-blind primary treatment period at each visit (i.e. Visit 4, 5, 6 and 7) and will not be conducted for time point after Visit 7.

For safety analysis, summary statistics will be provided for each arm during the both doubleblind primary treatment period (i.e. Visit 3 to 7) and entire study period (i.e. Visit 3 to 13). Table GBGF 5.1 gives the treatment groups to be displayed for each treatment period.

Unless otherwise specified, all tests of treatment effects will be conducted at a 2-sided alpha level of 0.05, and confidence intervals (CIs) will be calculated at 95%, 2-sided. All tests of interactions between treatment groups and other factors will be conducted at a 2-sided alpha level of 0.10. There will be no multiplicity adjustment for pairwise treatment comparisons.

List of analysis (LOA) will contain the list of all tables, figures and listings (TFLs), and will be provided separately.

			Between-Group Comparison When
Treatment Period	Treatment Groups	Abbreviation	Applicable
Double-blind	Placebo	Plc	Dula vs Plc

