#### 5.14. Safety Analyses

Unless otherwise specified, the safety analysis set will be used for analyses of safety measurements. Also, p-values provided from all safety analyses will be used for guidance purposes only.

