## 5.14.3. Hypoglycemic Episodes

A listing of the individual hypoglycemic episodes by patient will be presented.

Summary reports will include both incidence and rates of hypoglycemia using safety analysis set. Hypoglycemia will be analyzed as "documented symptomatic," "asymptomatic," "probable," "severe," or "nocturnal" and for all events combined, "total hypoglycemia." See protocol section 7.4.1.2. Other categories, including the categories above defined with differing PG thresholds, may also be included in these analyses when deemed appropriate. The incidence of hypoglycemic episodes will be compared using Fisher's exact test. Hypoglycemia rates will be summarized for periods of 1 year, 30 days, and 100 years (severe hypoglycemia only). The rate of severe hypoglycemia per 100 years will be compared between treatment groups using the empirical method (see Appendix 1). For each of the other categories of hypoglycemia, the number of hypoglycemia events during a specific period (rate) after randomization (for example, 0-16 weeks of treatment period) will be analyzed by using a negative binomial regression model. The model will include treatment and the baseline hypoglycemia rate (measured during lead-in) as a covariate. An offset defined as the log transformation of treatment exposure in the specific period (days)/365.25 days (or 30 days) will be included in the model to estimate the rate of hypoglycemia per year (or per 30 days). The proportion of patients with at least 1 hypoglycemic event in each category (incidence) during a specific period after randomization will be analyzed using a logistic regression model including treatment and baseline hypoglycemia rate value in the model.

Time to the first onset of total hypoglycemia and time to glucose-lowering intervention due to severe, persistent hyperglycemia will be analyzed between the groups using the semi-parametric proportional hazard regression model with treatment, baseline HbA1c (<8.5%,  $\geq8.5\%$ ), insulin regimen (basal insulin, premixed insulin, or basal/mealtime insulin) as fixed effects and baseline hypoglycemia rate (measured during lead-in) as a covariate. A Kaplan-Meier curve will be plotted for all treatments on the same graph, for presentation purposes. The proportion of patients that required intervention will be analyzed using Fisher's exact test.

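### SAP Appendix 1, equation (2), as it reads, gives the severe hypoglycemia p-value as 2Φ(|z|), which is never below 1 and contradicts the 95% interval when |z| exceeds 1.96

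*SAP*

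**What the plan says.** Protocol section 10.3.4.3 plans a comparison of severe hypoglycemia rates by the empirical method and leaves the details to the SAP. SAP section 5.14.3 then states: "The rate of severe hypoglycemia per 100 years will be compared between treatment groups using the empirical method (see Appendix 1". Appendix 1 is therefore the only specification of this test.

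In the part of Appendix 1 on event rates without strata, interval (1) is a normal-theory interval on the log rate ratio, using the 1 − α/2 normal quantile and then exponentiated. Equation (2) gives the p-value for a rate ratio of 1. In the text read from the PDF it begins "p = 2\Phi\left(\left|\log(\hat{\lambda", with the absolute log ratio divided by its standard error, and the line below it says that Φ "is cumulative distribution function of the standard normal distribution".

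The stratified version refers back to the same formula: "the p-value can be constructed similarly using (1) and (2) as for the ratio rate without strata". The cross-over version also cites (1) and (2).

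Two general rules bear on how the result is read. SAP section 5.2 says that, unless otherwise specified, "all tests of treatment effects will be conducted at a 2-sided alpha level of 0.05", with 95% two-sided intervals. SAP section 5.14 says that "p-values provided from all safety analyses will be used for guidance purposes only", and Protocol section 10.3.4 says the same.

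**The concern.** A two-sided normal p-value is twice the upper-tail area beyond the absolute test statistic. Equation (2), as it reads, takes twice the lower-tail area instead. The definition of Φ directly below it closes off the reading that Φ means the upper tail. The result is not a p-value: it cannot be less than 1, and it moves in the wrong direction.

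A programmer who follows the SAP literally would report an impossible number. One who silently corrects it would depart from the SAP. Wherever interval (1) excludes 1, the two outputs for the same comparison would disagree. Choosing the stratified version does not help, because it uses the same equation.

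**Working it through.** **Inputs.** Equation (2), interval (1) and the definition of Φ come from SAP Appendix 1; the two-sided 0.05 level and 95% intervals from SAP section 5.2; the arm sizes (40 placebo, 120 dulaglutide) from SAP section 5.1. The documents give no worked p-value and no expected rate of severe hypoglycemia, so there is no figure of the plan's own to reproduce here.

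**Step 1: range of the formula.** Let z = |log λ̂| / √Var(log λ̂). Since z ≥ 0, Φ(z) ≥ 0.5, so 2Φ(z) lies between 1 and 2. Also 2Φ(z) = 2 − 2{1 − Φ(z)}, that is, 2 minus the valid two-sided p-value.

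**Step 2: values.**

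| z | Equation (2) as read, 2Φ(z) | Valid p, 2{1 − Φ(z)} | Does 95% interval (1) exclude 1? |
|---|---|---|---|
| 0 | 1.000 | 1.000 | no |
| 0.5 | 1.383 | 0.617 | no |
| 1 | 1.683 | 0.317 | no |
| 1.96 | 1.950 | 0.050 | boundary |
| 2.5 | 1.988 | 0.012 | yes |
| 3 | 1.997 | 0.0027 | yes |

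Up to z = 1.96 neither output rejects, and only the reported p-value is wrong (at z = 0 the two formulas coincide). Above 1.96 the interval excludes 1 while equation (2) still cannot reject.

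**Step 3: two illustrations with assumed counts.** Assume 16 weeks (112 days) of exposure for everyone and at most one event per patient. Exposure is 40 × 112/365.25 = 12.27 patient-years on placebo and 120 × 112/365.25 = 36.80 on dulaglutide. Following Appendix 1, Var(log λ̂) = n₀S₀²/Y₀² + n₁S₁²/Y₁², with S² the sample variance of the 0/1 counts (divisor n − 1).

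(a) Two events in each arm (16.3 and 5.4 per 100 patient-years).
- S₀² = 2 × 38/(40 × 39) = 0.0487 and S₁² = 2 × 118/(120 × 119) = 0.0165.
- Variance = 0.487 + 0.496 = 0.983, so SE = 0.991.
- Ratio = 0.333 and z = log(3)/0.991 = 1.108.
- Interval (1): 0.048 to 2.327.
- Equation (2) as read: 1.73. Valid p: 0.268. Neither rejects.

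(b) Four events on placebo and two on dulaglutide (32.6 and 5.4 per 100 patient-years). The high placebo count was chosen only to take z past 1.96.
- S₀² = 4 × 36/(40 × 39) = 0.0923.
- Variance = 0.231 + 0.496 = 0.727, so SE = 0.852.
- Ratio = 0.167 and z = log(6)/0.852 = 2.102.
- Interval (1): 0.031 to 0.886, which excludes 1.
- Equation (2) as read: 1.96. Valid p: 0.036. The two outputs disagree.

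**Step 4: the corrected form.** With 2{1 − Φ(z)}, p < 0.05 exactly when the 95% interval (1) excludes 1.

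**The case against.** The strongest objection is that the whole point turns on one missing minus sign, or a missing 1 −, in an equation converted from PDF to text. The contents list of the SAP is visibly garbled by the same conversion. In the cross-over part of the appendix, the sentence introducing a new symbol shows the same symbol twice, so a small mark may have been lost there too. This stands as a reason to look at the source page first. Against it, the leading minus in interval (1), directly after an opening bracket, came through intact in the same part of the appendix. The form with 1 − would need several symbols to have vanished from an otherwise well-formed expression.

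The second objection is that little depends on this p-value. No success criterion is tied to it, safety p-values are for guidance, and any statistician would recognise the intended test from interval (1). There is no evidence that a program uses the formula as it reads. All of this is fair and limits the severity; it does not make the formula right.

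Third, equation (2) may never be evaluated, because log λ̂ is undefined if either arm has no event. Exclusion criterion 17 removes patients with recent severe hypoglycemia, and sulfonylureas and glinides are washed out. At the dulaglutide rate assumed above (2 in 120 patients), 40 placebo patients would have no event with probability (118/120)^40 = 0.51. That lowers the chance that the error shows, but the SAP still prescribes the comparison.

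Finally, the counts in the illustrations are invented, and (b) needs 10% of placebo patients to have an event (4/40). The algebra in Step 1 does not depend on them.

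**Conclusion.** The concern holds. As it reads, equation (2) cannot give a valid p-value except in the trivial case z = 0; it returns 2 minus the correct value for every data set, and it contradicts the 95% interval (1) whenever z exceeds 1.96. Nothing elsewhere in the SAP corrects it.

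The severity is minor. One secondary safety comparison is touched, and the error cannot produce a false claim of significance. Interval (1), the rates in each arm and the incidence analyses in section 5.14.3 are unaffected, as are all efficacy analyses. Confidence is medium, solely because the conclusion assumes that the source page reads as the extracted text does.

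**What to change.** Check equation (2) against the source page of the SAP. If it reads as above, replace it with p = 2{1 − Φ(|log λ̂| / √Var(log λ̂))}, equivalently 2Φ(−|log λ̂| / √Var(log λ̂)), and confirm that the analysis program computes this. The later references to (2) in Appendix 1 then need no edit of their own.

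The cost is one corrected formula and one program check. Data, conduct and all other analyses stay as they are.
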